CBTi is an effective skill-based psychotherapy for insomnia. The American College of Physicians (ACP) issued new practice guidelines stating that "Cognitive behavior therapy should be the initial treatment option in persons with chronic insomnia." CBTi improves sleep among middle aged and older adults without comorbidities, among patients with psychiatric and medical comorbidities, and among patients with hypnotic dependence. Importantly, CBTi has more durable benefits than hypnotic medications among midlife and older adults. CBTi can reduce the use of sleep medication for two reasons: (a) it can be offered as an alternative to hypnotics as an initial treatment option; and (b) it can facilitate reduction or discontinuation of sleep medications for those already taking them. Reduction/discontinuation of hypnotic use during CBTi can be indirect (i.e., some patients spontaneously reduce their use as they acquire new skills) or direct (i.e., therapist assisted), particularly when the CBTi protocol includes a specific module to address medication taper/discontinuation.

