There is a major gap between the current state of the science and actual clinical practice: Limited access to CBTi is a major barrier to its wide-scale use as a first line treatment insomnia and ergo to the implementation of the ACP guidelines. Current models of therapist-led delivery are a major limiting factor in treatment access, largely due to the low number of trained providers relative to those needing treatment (largely due to the low number of trained providers relative to those needing treatment). Pilot studies have examined alternatives to traditional therapist-led delivery methods, such as abbreviated CBTi and delivery using telehealth among older adults; it is unlikely that, even if the results from these pilot tests are proven effective in large-scale trials, they alone can meet the demand for insomnia treatment in primary care. Another approach to increasing access to CBTi is to thoughtfully utilize consumer directed CBTi products, such as online programs. Such products offer patients a convenient way to receive treatment that addresses several barriers to therapist led-CBTi, including geographic, mobility, scheduling constraints, reduced waiting time for therapy, reduced stigma and embarrassment in seeking help, flexibility in accessing self-paced treatment, and efficient use of resource within the healthcare system. However, online CBTi programs have limitations. They are less effective than in-person treatment, with effect size for reduction in insomnia severity being half of the effect size following in-person therapy (Cohen d = 1.2 vs 2.3). In addition, online CBTi programs have high dropout rates (low engagement) that may contribute to lower efficacy. Current online CBTi programs are not the best choice when the goal is to reduce frequent use of hypnotic medications because they do not include modules to support the often difficult process of discontinuing these medications. (Although, through improving sleep, online CBTi can lead to hypnotic discontinuation among some users, effect sizes are smaller than therapist-led CBTi.) Online CBTi programs also do not include modules to address circadian rhythm factors, such as those present among individuals with unusual sleep schedules. Individuals who, based on past research on CBTi are at increased risk for dropping out from therapist-led CBTi are likely at even greater risk for dropping out from or online CBTi programs, since they lack flexibility in tailoring the intervention to support adherence.

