
STEPPED-CARE CBTi has strong potential for overcoming the shortcomings of an online only approach, while maintaining the scalability advantages offered by an online CBTi.

b. Findings from Past Animal Experiments

Not applicable.

4. **NVESTIGATIONAL DEVICES**

| Investigational Device 1 | |
|--------------------------|--|
| Name: | Sleepio |
| Description: | Sleepio is an online consumer program. There is no device involved. |
| | However, participants can get a free app to have access to some aspects of |
| | the program on their personal device if they so choose. |

5. **PARTICIPANT POPULATION**

a. Planned Enrollment

This is a single site study. We hope to randomize 240 middle aged and older adult patients with insomnia disorder

b. Age, Gender, and Ethnic Background

Age: 50 and older Gender: all ethnicity: all

c. Vulnerable Populations

Recruitment will NOT target potentially vulnerable populations; but they will not be excluded.

d. Stanford Populations

Recruitment will NOT target laboratory personnel, employees, and/or students; but they will not be excluded

e. Healthy Volunteers

Healthy volunteers will not be included.

f. Recruitment Details

Patients will be recruited from primary care clinics that are part of the Stanford Health care system. Patients will be identified as potentially eligible through a search of electronic health records. The search will be based on age, insomnia diagnosis or use of sedative hypnotics, and the absence of a diagnosis of dementia or the need for an interpreter; all of which can easily be extracted from the electronic medical records. Those identified will be invited to participate, using a Myhealth message (scripts for SHC clinics and for SHA are attached). The SHC MyHealth message will be sent on behalf of individual primary care clinic providers/directors and the protocol director who have given their explicit permission for us to do so.

The MyHealth message for SHA will be sent on behalf of [name], Chief Medical Officer, University Healthcare Alliance, and the Protocol director, who has given us permission to do so.

Patients without an active MyHealth account will be sent a letter via mail. This letter will have the identical content as the attached MyHealth scripts on a departmental letter head.

The attached script includes a link to a contact form which is also attached, and a study website

Those who respond to the invitation will be phone screened.

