In addition, patients may contact us by responding to IRB approved advertisements, through brochures, flyers, and electronic media. Patients who contact the study team directly will be considered for inclusion, even if they do not receive care at the Stanford health care system.

g. Eligibility Criteria

- i. Inclusion Criteria
 - Age>=50
 - Meets criteria for insomnia disorder
 - Residing in California
 - Has primary care provider in California
- ii. Exclusion Criteria
 - Cannot be consented in English without an interpreter
 - Does not have a reliable telephone service
 - Lack physical or mental capacity to participate in treatment. Examples include, but are not limited to, thought disorder and Cognitive impairment (mini mental status exam score < 25).
 - Presence of alcohol use disorder or drug use disorder, excluding sedative hypnotic or anxiolytic (taken for sleep), with current withdrawal symptoms or if severe (per DSM-5);
 - Use of substances that cause sleep disturbances (e.g., stimulants, prednisone)
 - Family member that resides in same household as another study participant
 - Inability to use and cannot get help from a trusted other for using the internet daily.
 - The study physician determines their participation is not medically advised for any reason.
 - Does not currently receive CBTi

h. Screening Procedures

Participants will begin screen with a telephone screen or a self-administered online screening checklist (both uploaded). Those not excluded will undergo two structured clinical interviews conducted by trained research personnel: 1) the Duke Structured Interview for Sleep Disorders (DSISD) for ascertaining insomnia and documenting other sleep disorder diagnoses; 2) the widely used Structured Clinical Interview for DSM Disorders (SCID), MINI version to assess severe unstable comorbid psychiatric conditions that might better explain the insomnia symptoms; 3) the Folstein Mini-Mental Status Exam (MMSE). These questionnaires and interviews are attached. 4) For consented participants, who the study physician identified as medically complex (e.g., taking more than 10 prescription medications), we will request medical clearance from their PCP; (for those receiving care outside we will use the attached letter.)

i. Participation in Multiple Protocols

Participants will be asked if they are currently participating in another study. When a potential participant reports participating in another study where there is a potential for

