Randomized Controlled Study of the Effectiveness of Stepped-Care Sleep Therapy In General Practice

NCT03532282

December 9, 2024

Data Analysis Plan for Primary AIM 1 (as originally proposed in the NIH grant application)

All analysis will be for the intent to treat sample.

For the primary outcomes we hypothesized that, compared to ONLN, participants in STEP would have greater reductions in the two co-primary outcomes, insomnia severity (Hypothesis 1a) and use of prescription sleep mediations (Hypothesis 1b). Together these two hypotheses test whether the triaged stepped care strategy is superior to having access to only dCBT-I over one year.

Repeated measures mixed-effects linear model will be used with experimental group (STEP or ONLN) and time (6 assessments: at baseline and at months 2, 4, 6, 9, &12), and their interactions as fixed effects. Of interest for these analyses are the effects of these factors on the trajectory of individual responses. The group effect size on the slope (Group X Time) is the average group effect, ignoring strata, testing whether there is a difference in the response trajectories between the STEPPED CARE and ONLINE ONLY approaches. For hypothesis 1a the dependent variable is the ISI and for hypothesis 1b the dependent variable is use of prescription sleep medications.

For the secondary outcomes we hypothesized that, compared to ONLN, participants in STEP would have greater reductions in sleep related impairment (hypothesis 2a) and psychological distress (hypothesis 2b).

Repeated measures mixed-effects linear model will be used with experimental group (STEP or ONLN) and time (6 assessments: at baseline and at months 2, 4, 6, 9, &12), and their interactions as fixed effects. Of interest for these analyses are the effects of these factors on the trajectory of individual responses. The group effect size on the slope (Group X Time) is the average group effect, ignoring strata, testing whether there is a difference in the response trajectories between the STEPPED CARE and ONLINE ONLY approaches. For hypothesis 2a the dependent variable was the PROMIS sleep related impairment and for hypothesis 2b the dependent variable was PHQ-4.

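### Co-primary H1b leaves out baseline medication use by time, so the all-patient slope test loses precision that baseline data could recover; the loss may be small and is not a bias

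*SAP*

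**What the plan says.** The SAP (Data Analysis Plan for Primary AIM 1) analyses everyone as randomised. Hypothesis 1b predicts a larger reduction in prescription sleep-medication use under STEP than under ONLN. On the model it says: "Repeated measures mixed-effects linear model will be used with experimental group (STEP or ONLN) and time", plus their interaction. It adds that "for hypothesis 1b the dependent variable is use of prescription sleep medications" and that the Group X Time slope "is the average group effect, ignoring strata". It gives no scale for use, no baseline-use term and no result for baseline users alone.

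The Protocol does not restrict entry to users. In section 5(g) the clinical entry criterion is "Meets criteria for insomnia disorder", and none of the four inclusion criteria asks for medication use. In 5(f), "The search will be based on age, insomnia diagnosis or use of sedative hypnotics", so a diagnosis without medication is enough for an invitation. People who answer advertisements can also enter.

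Section 3(a) gives CBTi two routes to lower use. It can help current users cut down or stop, and "it can be offered as an alternative to hypnotics as an initial treatment option". The second route is how a non-user could contribute to H1b.

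**The concern.** A patient who enters at zero use can only stay there or start. A baseline user can fall. The two groups will therefore tend to have different average slopes whatever the arm, and user status is known before treatment. A model without user status by time treats that predictable difference as unexplained variation between patients, and the standard error of the Group X Time coefficient carries it.

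At stake is the precision of one of two co-primary tests. A separate matter is how the result reads. If non-users rarely start, the all-patient coefficient is roughly the effect in users multiplied by the share of users. A small slope could then mean a weak effect or few users enrolled, and the AIM 1 plan reports nothing that would tell these apart.

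**Working it through.** **Nothing to reproduce.** The documents give no power calculation, alpha, effect size or user share for H1b. Section 5(a) of the Protocol gives a target of 240 randomised. The visits (months 0, 2, 4, 6, 9, 12) come from the SAP. Everything else below is assumed, including 1:1 allocation and a two-sided 0.05 level.

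**Mechanism.** With complete data and linear time, the random intercept-and-slope estimate of Group X Time equals a regression of each patient's slope on group (12 fits, difference below 1e-13). Let p be the share of users. Put slopes in units of the users' slope SD, with users' mean change μ and non-users' mean change 0 and SD s. Then:

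- slope variance without the term: p + (1−p)s² + p(1−p)μ²
- slope variance with user status by time: p + (1−p)s²
- SE = √(4 × variance / 240)

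Example with p = 0.5, s = 0.3:

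- The variance with the term is 0.5 + 0.5 × 0.09 = 0.545.
- If μ = 0.5, the removable part is 0.25 × 0.25 = 0.0625. The gain is 0.0625/0.545 = 11%, as if 240 patients were 268.
- If μ = 1, the removable part is 0.25. The gain is 0.25/0.545 = 46%, as if 240 were 350.

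Over p = 0.3 to 0.7 and s = 0 to 0.6, the SE is multiplied by 0.92 to 0.97 at μ = 0.5 and by 0.77 to 0.89 at μ = 1. The gain depends mainly on how far users change on average, which the documents do not give.

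A main effect of user status alone shifts a patient's level, not the slope. With complete data it leaves the Group X Time estimate exactly as it was.

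**Simulation on a bounded scale.** Assumed: 120 per arm, 0–7 nights per week, users at 2–7 nights at baseline, visit noise SD 1 night, complete data, 4,000 replicates per cell, HC3 standard errors. Triplets are for 30/45/60% baseline users.

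| Scenario, ONLN vs STEP | Variance gain, % | Power without | Power with | Rise, points |
|---|---|---|---|---|
| Stop 5% vs 20%; 5% start | 9/7/5 | 0.23/0.36/0.51 | 0.24/0.39/0.53 | 1/3/2 |
| Stop 10% vs 25%; 2% start | 11/11/8 | 0.21/0.33/0.45 | 0.22/0.36/0.48 | 1/3/3 |
| Stop 25% vs 45%; 2% start | 28/21/14 | 0.24/0.35/0.48 | 0.28/0.41/0.54 | 4/6/6 |
| Stop 25% vs 35%, nights cut 10% vs 35%; 2% start | 52/46/33 | 0.36/0.55/0.73 | 0.51/0.71/0.85 | 15/16/12 |

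Check on one cell (third row, 30% users): the SD of the 12-month effect is 0.213 without and 0.189 with the term, and (0.213/0.189)² = 1.27, which agrees with 28% up to rounding. A separately written simulation of the last three rows (3,000 replicates) gave gains of 10/7/5, 23/20/16 and 51/37/31%. Its power rises were 1/2/3, 4/7/5 and 12/15/11 points. If the metric is yes/no use at each visit, the gain is 7–33%.

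**Validity.** With no arm difference, rejection was 0.048/0.048/0.052 without the term and 0.051/0.054/0.047 with it.

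**Amount instead of status.** In two further complete-data runs, baseline amount by time gained 9–38% against 4–24% for user status, and 11–66% against 5–46%. The mean treatment effect was unchanged (within 0.004 nights in the first run).

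**User mix.** If 10% vs 25% of users stop, the effect in users is about −0.66 nights. Multiplied by 0.30, 0.45 and 0.60, it gives −0.20, −0.30 and −0.40 nights in all patients.

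**The case against.** The strongest reply is that the plan contains no error. The randomised all-patient contrast is valid, and it answers the question the SAP poses, which compares two care strategies. Section 3(a) of the Protocol gives non-users a place in that question. All of this stands.

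The second reply is that the gain may be trivial. Section 3(a) says of online programs that "they do not include modules to support the often difficult process of discontinuing these medications", so few ONLN users may stop, and in the few-stop rows power rises by only 1 to 3 points. In all three rows without cutting down, power lies between 0.21 and 0.54 with or without the term. The larger gains need a scenario that the documents neither support nor exclude. This also stands, and it limits the importance of the point. It does not remove it, because the term costs almost nothing.

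The third reply is that the adjusted coefficient still depends on the user share. That is correct. The added term buys precision only; a separate contrast among users is what helps interpretation.

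A fourth is that the metric must be settled first. That is true, and it is part of the fix.

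One further argument does not stand. A reader might hold that baseline amount must be barred because baseline is also in the outcome. User status comes from the same measurement, and with a yes/no metric it is the baseline outcome itself. The complete-data runs showed no shift in the effect with amount.

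**Conclusion.** The point holds as a loss of precision in one co-primary test. The SAP's H1b model omits a baseline-use-by-time term although the Protocol lets non-users in. Under the stated assumptions the term is worth roughly 5 to 50% in variance. The power gain runs from 1 to 3 points when few users stop to about 11 to 16 when users also cut down. User share, metric, stopping and starting rates and allocation are all assumed, so the documents alone do not fix where in that range the trial lies.

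Three stronger readings are tempting and not supported:

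- **The H1b test is biased or has an inflated type I error.** Randomisation protects the contrast, and null rejection stayed near 5%.
- **The all-patient effect is the wrong target.** The Protocol's own rationale includes offering CBTi instead of starting a hypnotic.
- **The strata set aside in the SAP include baseline medication use.** Neither document defines them.

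No gain is claimed under dropout. Section 3(a) says that "online CBTi programs have high dropout rates (low engagement) that may contribute to lower efficacy", but no rate is given, and the figures above assume complete data.

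**What to change.** Keep the intent-to-treat sample, the linear mixed model and the all-patient Group X Time test as co-primary. Then:

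1. State the metric for medication use in advance (for example, nights per week).
2. Add one prespecified baseline-use covariate, either user status (yes/no) or baseline amount, **and** its interaction with time, with robust standard errors. With complete data either choice leaves the treatment effect unchanged on average, and amount gains at least as much.
3. Because both covariates derive from the baseline measurement, run as a check a version with baseline removed from the outcome and used only as a covariate.
4. Report the same contrast among baseline users, labelled supportive only.

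Specify this before H1b is compared by arm. The SAP is dated December 9, 2024; if that comparison has already been made, label the adjusted model a sensitivity analysis.

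The cost is two model terms, a sentence on the metric, one check and one supportive table. Baseline is already one of the six assessments, so no new data are needed, and the sample, hypothesis and target effect stay the same. The downside is slightly more analysis work for a gain that may be small.
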